**Figure 2. Table of Variables/Data Points**

Variable	Data Source
Age	Patient report
Race	Patient report
Gender	Patient report
Height and Weight	Essentris or Ahlta
Pain scores	Patient report and Essentris
Pre op and PACU pain scores	Essentris
Total time in OR	Essentris
Surgical date	Patient report, confirmed in S3
Total OR time	Essentris
Needle retention time	Documented by the PI
Type of Surgery	Essentris
Needle type	Documented by the PI
Intraoperative anesthetic	Essentris
Dexamethasone dose	Essentris
Total Morphine Equivalent	Essentris and John Hopkins Converstion
Daily pain scores	Home diary
Post op Nausea/Vomiting	Essentris notes
Day diet returned to normal	Home diary
Oral pain meds at home	Home diary

**7.4 RISKS TO SUBJECTS:** Acupuncture is considered a safe technique with minimal risk to the subject. Acupuncture needles only penetrate the skin approximately one millimeter. Despite the minimal penetratruion, needle insertion poses the risk of infection, bleeding and bruising. All acupuncture needles used in this study will be sterile and inserted after alcohol preparation of the ear surface. The needles are made of gold and pose minimal, if any, allergic reaction.

IRBNet Number: 381600-19

PI: [name]

Protocol Title: **A randomized, single-blind, prospective trial of auricular acupuncture for the reduction of post-operative tonsillectomy pain in adults.**

Initial Date Submitted: 6/13/2013

Revision Date: 7/17/17

**8.0 DATA ANALYSIS:** The primary metric for this study is pain score. Pain scores will be collected for 10 days post-operatively, as previous studies have demonstrated a return to baseline by this time. Pain scores will be collected daily during this time period, resulting in repeated measures for each subject. Analysis will be conducted by mixed models to evaluate both (1) difference in pain scores by groups and (2) rate of change in pain score over time.

Age and sex will be considered as potential confounders. Duration of needle insertion may also be evaluated for effect on outcome, if significant variability in length is noted. The type of surgical technique (cold knife coblation versus cautery) may be a potential confounder. Finally, intra-operative anesthesia and dexamethasone dose will be evaluated for potential confounding.

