**J. I must submit to the Clinical Investigation Service (CIS):**

- i. Any source of outside funding.
- ii. An annual Continuing Review Report (CR), due in the anniversary month of the protocol's initial approval or due in the month as determined by the IRB for continuing review and approval.
- iii. Reports of adverse effects occurring in subjects as a result of study participation or of any protocol deviations and submit these reports to Research Monitor if there is one for the study.
- iv. An Addendum, prior to any changes made to the study or a change in the funding status.
- v. Listing of presentations, abstracts, and publications arising from the study for inclusion in the CR.

**K. I will maintain a Study File that must be kept for six years following completion of the study if no IND/IDE used (32 CFR 219.115(b)). If IND medication or IDE appliances are used, the file must be kept for 2 years after FDA approval and can then be destroyed; or if no application is filed or approved, until 2 years after the study is discontinued and FDA notified (21CFR 312.62(c)). The records should be kept in the Department/Service where the research took place (AR 40-38). If I am scheduled to PCS or ETS, I will notify the Clinical Investigation Service as soon as I am aware but at least 3 months prior to departure. Records will be given to a new WAMC PI or the Department/Service Chief.**

**L. I will be familiar with all applicable regulations governing research, and will adhere to all of the requirements outlined in the WAMC's DOD Assurance and Federal-Wide Assurance granted by the Office for Human Research Protections, Department of Health and Human Services.**

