Many different acupuncture techniques are commonly used for managing pain; specifically, auricular acupuncture has been a long-standing therapeutic modality dating back thousands of years. The use of auricular acupuncture has been applied to many conditions including headache, allergic rhinitis, chronic fatigue, anxiety and pain. The hypothesized efficacy of auricular acupuncture comes from the premise that the external ear represents a microsystem of the entire body. The ear serves as a miniature homunculus, whereby specific points on the ear correspond to specific areas of the body. A modified technique, referred to as Battlefield Acupuncture (BA), was developed by [name] in 2001 and utilizes only five major auricular points (see Figure 1). [name] collaborated with a neurophysiologist to determine which areas of the brain were activated in patients experiencing pain. They utilized functional MRI to visualize these pain centers and found less activity in these areas after the application of auricular acupuncture. BA is an appealing method of analgesia since it can be easily taught, easily applied, does not require highly specialized equipment or sterile operating conditions, and is inexpensive. Furthermore, its risks are minimal, including irritation or possible infection of the ear. To our knowledge, this is the first single-blinded, prospective, randomized trial evaluating the efficacy of BA in reducing post-operative pain for adult tonsillectomy.

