- If screening criteria based on inclusion and exclusion criteria are not met the potential participant will be thanked for their time and informed that they do not qualify for the study.
- If the patient meets the screening criteria and verbalizes interest in participating in the study, he or she is notified that s/he can be scheduled to further review and complete the consent paperwork if s/he wishes with study staff when s/he is present for the pre-admission appointment or at another time convenient for the potential participant. Then, at that time, the potential participant will have a chance to review any questions s/he may have about the study and complete the study consent paperwork if s/he wishes to participate. Consenting will take place in advance of the day of the procedure; if possible and if not a team member will meet with potential participant on the day of surgery in holding. Once a subject has consented to be in the study, the individual consenting them will interview them for demographics, medical history, medication history, and allergies (Appendix A). The pain diary will be reviewed at this time as well. If the subject is determined to be eligible for the study, her/his scheduled date of surgery will be confirmed. The PI will keep a list of all subjects and their respective surgery dates in a password protected electronic enrollment log kept in the V drive.
- **Home diary teaching:** At the Pre admit and/or consent appointment, a research team member will review the home pain diary with the subject. They will be asked to record their pain score in 6 hour intervals for 24 hours after hospital discharge and every 24 hours for a total of 10 days after the surgery. Subjects will not be asked to wake up at night to record pain level. Subjects will be asked to return their pain scores by phone, email, or mail (addressed envelope provided). If the subject has not sent their diary by day 15, an attempt at a reminder to the subject via phone call or email (whichever the subject prefers, as collected during enrollment) will be done. .
- **On the day of the surgery:** On the day of surgery, the randomization category will be determined by the PI or AI acupuncturists by opening the corresponding subject number envelope. Prior to surgery, the PI or AI acupuncturists will introduce him or herself to the subject (if not already done so) and confirm enrollment in the study. Anesthesia for the surgical case will then proceed per standard of care.

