IRBNet Number: 381600-19

PI: [name]

Protocol Title: **A randomized, single-blind, prospective trial of auricular acupuncture for the reduction of post-operative tonsillectomy pain in adults.**

Initial Date Submitted: 6/13/2013

Revision Date: 7/17/17

After the patient has been fully anesthetized, and prior to the start of the tonsillectomy, the study PI or AI acupuncturists will place the acupuncture needles if randomized to the acupuncture group. Initiation of the surgical case will not be delayed for acupuncture needle placement. If the patient is randomized to the control group, no intervention will occur.

The procedure for the auricular acupuncture is standardized based on the Battlefield Acupuncture technique. The ear will be cleaned with alcohol prior to insertion of the needles. Five sterile, single-use, gold needles will be placed in each ear according to the figure below. The needles penetrate about a millimeter (or 4/100ths of an inch) into the skin.

Figure 1. Five points of Battlefield Acupuncture

At the end of the surgical case, prior to fully awakening the patient, the PI or his designee will remove the acupuncture needles.

Per standard of care, the providing anesthesiologist or PACU nurse will document in Essentris the subject's pain score every 15 minutes for one hour and then hourly until discharge from the PACU. A pain score will also be recorded in

IRBNet Number: 381600-19

PI: [name]

Protocol Title: **A randomized, single-blind, prospective trial of auricular acupuncture for the reduction of post-operative tonsillectomy pain in adults.**

Initial Date Submitted: 6/13/2013

Revision Date: 7/17/17

Essentris when prescribed as needed (PRN) pain medications are requested.

Anesthesia and pain medication will be provided per standard of care by the anesthesiologist assigned to the surgical case. All medications given will be documented in Essentris. All discharge instructions by the surgeon and anesthesiologist will be per standard of care.

PACU nurse education will be per standard of care only; the PACU nurse will not be responsible for any study education.

Data will be collected by the PI, AIs, on the day of surgery and recorded on the form found in Appendix B.

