**Data collection:** Data will be collected and entered into three forms (Appendices A-C). All forms will be maintained in a locked file cabinet in the PI's locked office. Data will be collected during the initial subject interview by the individual consenting them (Appendix A), on the day of surgery by the PI (Appendix B), and from the home pain diary. (Appendix C). Data on the day of surgery may also be collected from Essentris or the anesthesia record once the patient has been discharged (as all data needed will be recorded in Essentris or the anesthesia record). Data will be transferred from these forms to an electronic Data base. Each patient will be allocated a study ID number, and thereafter will be referred to by that number in the database. An Excel spreadsheet with all current data will be where the data is to be entered by a research team member. It will be maintained in the V drive with limited password access. Only research team members will have access.

- Total doses of opioid analgesics in the preoperative, intraoperative and postoperative period will be converted to IV morphine equivalents by the PI or research staff member. They will use John Hopkins Opioid Program's conversion at <http://www.hopweb.org/hop/hop.cfm>
- **Acupuncture Competence:** The PI completed the 300 CME Helms Medical Acupuncture Course, the DOD wide approved acupuncture course.

• **Data Collection Instrument:**

- **Appendix A: Data collection form for demographic and contact information to be collected after initial consent prior to surgery**
- **Appendix B: Data form for day of surgery data collection**
- **Appendix C: The home diary to be completed by the subject**

• **Other Appendices**

- **Appendix D: Flow chart of recruitment to discharge**
- **Appendix E : Screening inclusion/exclusion**
- **Appendix F: Script for MSA's (Medical Support Assistants)**

IRBNet Number: 381600-19

PI: [name]

Protocol Title: **A randomized, single-blind, prospective trial of auricular acupuncture for the reduction of post-operative tonsillectomy pain in adults.**

Initial Date Submitted: 6/13/2013

Revision Date: 7/17/17

- **Appendix G: Optional Research Packet (flyer/information sheet/envelope)**
- **Appendix H: Data Excel**

• **Variables/Data Points:**

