**vi. Will research data including identifiable Protected Health Information be sent outside of**

IRBNet Number: 381600-19

PI: [name]

Protocol Title: **A randomized, single-blind, prospective trial of auricular acupuncture for the reduction of post-operative tonsillectomy pain in adults.**

Initial Date Submitted: 6/13/2013

Revision Date: 7/17/17

WAMC?

Yes  
 No

vii. Linkage of extracted data to other databases: N/A

**12.1 BENEFITS:** Identification of a minimal risk intra-operative technique that minimizes post-operative pain benefits the healthcare system as a whole. Acupuncture is a relatively inexpensive and quick procedure. Implementation of this technique may reduce healthcare costs. Additionally, individual subjects may benefit from decreased post-operative pain and experience shorter recovery time.

**12.2 RISKS:** The only risk of data collection during the study is potential loss of privacy/confidentiality of enrollment in the study. The consents forms with the subject's name will be stored in a locked file cabinet in the anesthesia office area at WAMC. The master link between subject name and ID will be stored in a password protected Excel file on the V drive at WAMC, with access limited to only the study team. This file will be separate from the file containing the collected data.,

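### The plan names ear harms from needling but schedules no ear assessment, so they would surface only through passive, attribution-based reports and their absence could not be interpreted

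*Combined protocol and SAP*

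**What the plan says.** Section 7.4 states that "needle insertion poses the risk of infection, bleeding and bruising". The background in section 6.0 says of the technique that "its risks are minimal, including irritation or possible infection of the ear".

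Section 7.3 has five needles placed in each ear under anesthesia, ten sites per treated subject. At the end of the case, "prior to fully awakening the patient, the PI or his designee will remove the acupuncture needles". No inspection of the ear is described then or later. Controls receive no intervention.

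For home follow-up, section 7.3 says of subjects: "They will be asked to record their pain score in 6 hour intervals for 24 hours after hospital discharge", then daily to day 10. Figure 2 takes three things from the diary: daily pain, the day diet returned to normal, and oral pain medication. A reminder by phone or email is attempted only when the diary has not arrived by day 15.

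The needle items in Figure 2 are retention time and needle type. Its only harm-type variable is postoperative nausea and vomiting, taken from the hospital record. Figure 3 lists pain, diet and home opioid use, with no safety outcome.

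Two general reporting duties exist. Section 3.0 J(iii) requires the investigator to submit "Reports of adverse effects occurring in subjects as a result of study participation". Section 3.0 M provides for review of unanticipated problems, serious adverse events and deaths if a research monitor is assigned.

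**The concern.** A harm that the protocol itself names is not among the things it plans to observe. Infection would normally show itself after discharge, when the described follow-up asks about pain, diet and medication only. What remains is a chain: the subject or a clinician notices, someone tells the study, and the investigator judges the event to result from participation. Each link loses events. The last link also differs by arm, because a control subject was never needled and so has almost nothing that could be attributed.

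Section 12.1 rests its benefit statement on low risk: "Identification of a minimal risk intra-operative technique that minimizes post-operative pain benefits the healthcare system as a whole". Section 9.0 looks ahead to use in the operating room. If the trial reported no ear events, readers could take that as support for safety, although the plan was not set up to find such events.

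**Working it through.** The plan gives no safety figure to reproduce. The check has two parts.

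**1. Named harms against planned observation**

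| Named harm | When it could be seen | Planned item |
|---|---|---|
| Bleeding, bruising | At needle removal and after | None listed in Figure 2 |
| Irritation | Recovery and home | None listed |
| Infection | Mainly after discharge | None listed; diary items are pain, diet, medication |

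The only route for all of these is section 3.0 J(iii), with 3.0 M if a monitor is assigned.

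**2. What passive capture does to the information**

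Inputs: n = 45 acupuncture subjects (section 7.3 target). The true rate p and the share q of events that get reported are not in the documents. They are assumed, with p at 5% or 10% and q from 10% to 100%.

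Chance of at least one recorded event: 1 − (1 − pq)^45.

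- p = 5%, q = 100%: 1 − 0.95^45 = 90%
- p = 5%, q = 25%: 1 − 0.9875^45 = 43%

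| Share reported, q | p = 5% | p = 10% |
|---|---|---|
| 10% | 20% | 36% |
| 25% | 43% | 68% |
| 50% | 68% | 90% |
| 100% | 90% | 99% |

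One-sided 95% upper bound when all n are asked and none has an event: 1 − 0.05^(1/n).

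- n = 45: 1 − 0.05^(1/45) = 6.4%
- n = 62 (125 enrolled, even split assumed, all answering): 1 − 0.05^(1/62) = 4.7%
- n = 30 (assumed, to show the effect of non-response): 1 − 0.05^(1/30) = 9.5%

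With passive reporting, zero reports in 45 bound only the product pq at 6.4%. The bound on p is 6.4%/q, which is 12.9% at q = 50%, 25.8% at q = 25% and 64.4% at q = 10%. Since the plan gives no means of knowing q, no usable bound on p follows.

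**The case against.** The strongest reply is that the plan is not blind to ear harm. The investigator has a standing duty to report adverse effects, a monitor may review serious or unanticipated ones, and the person who takes the needles out is at the ear and can see immediate bleeding or bruising. All of this stands. A reader might infer that the trial would show no ear harm whatever the true rate. The documents do not support that: it would require zero capture, which the plan does not specify, and the table above shows a real chance of some reports at any capture above zero.

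A reader might also infer that no data form asks about the ear. That cannot be established. The forms are known by title only ("Appendix B: Data form for day of surgery data collection"), and the point rests on Figure 2 and the described procedures. Nor can one say that a subject has no reason to connect a sore ear with the study. Subjects agree to a trial of auricular acupuncture, and the consent text, which may tell them what to report, is not available here.

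It is also fair to say that section 7.2 sets no safety aim, that low risk is a premise of the plan and not a result it promises, and that section 9.0 speaks only of initial work. This limits the consequence but does not remove it: harms named in a protocol need a stated way of being counted, and passive reports have no sound denominator.

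Finally, an ear item printed in the diary would be seen at the diary teaching before surgery. It could prompt subjects to inspect their ears while still scoring pain, which is a threat in a single-blind trial with a self-reported primary outcome. That objection stands and determines where the question may be placed.

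**Conclusion.** The listed variables, the analysis table and the described follow-up contain no planned ear assessment and no general adverse-event item. Ear harm, especially infection after discharge, would be found only through passive reporting that depends on attribution. Its rate would probably be understated, a comparison between arms would be unfair by construction, and an absence of reports would not be evidence of safety. This cannot be repaired at the analysis stage.

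The size depends on the unknown reporting share. At an assumed 5% true rate, the chance of seeing any event among 45 falls from 90% with full capture to between 20% and 68% when 10% to 50% of events are reported. The conclusion assumes that Figure 2 reflects what the forms collect. If Appendix B or C already has an ear item, the gap narrows to adding it to Figure 2 and Figure 3. The pain analysis is not affected.

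**What to change.** 1. Have the person who removes the needles record visible bleeding or bruising (yes/no, per ear) on the day-of-surgery form. This covers the acupuncture arm only and is descriptive.
2. Ask one identical question in both arms: redness, swelling or discharge; bleeding; bruising; whether care was sought. Ask it only after the day-10 pain score, at diary return or at the existing day-15 contact, or on a separate sheet not shown at diary teaching.
3. Add ear events to Figure 2. Tabulate them by arm regardless of judged relatedness, with the number asked as denominator and an upper confidence limit. Pass positive answers to the investigator under section 3.0 J.

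Cost: about a minute per subject, one field, one question, one table and an IRB addendum. Recall at day 10 will be imperfect for early bleeding or bruising. Section 7.3 already calls diary return low, so the number answering may fall short of 45 and the bound would then be wider than 6.4%. Subjects already followed will have no data.

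Section 5.0 expects data collection to end in July 2017 and this revision is dated 7/17/17, so few subjects may remain, although sections 7.3 and 11.0 continue enrollment. If enrollment is effectively complete, state in the report that ear harms were not systematically ascertained, and draw no safety conclusion from their absence.

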## **10.0 MEDICAL APPLICATION:**

Over the last decade, the concept of multi-modal analgesia has been utilized in the treatment of acute post-operative pain. The American Society of Anesthesiologists published a practice guideline stating: "Whenever possible, anesthesiologists should use multimodal pain management therapy. Central regional blockade with local anesthetics should be considered. Unless contraindicated, patients should receive an around-the-clock regimen of COXIBs ( Cox-2 Inhibitors), NSAIDs (Non-Steroid Anti-inflammatory Drugs), or acetaminophen." The treatment of both acute and chronic pain has received national attention. Several media outlets have reported on the complex problem of adequately treating pain, while trying to minimize or eliminate the misuse potential of narcotic analgesics. Furthermore, in an environment where downsizing and costs savings are required, the potential to save money on medical management and reduced adverse side effect related problems will become a major part of military healthcare in the coming years. In 2009, Abbott Northwestern Hospital in Minneapolis conducted a retrospective observational study of the pain management effect of nontoxic, nonpharmacological integrative approaches among 1,839 in-patients to include acupuncture. Two thirds of subjects, mainly post-surgical, had never previously received integrative services. The immediate effect on self-reported pain scores was an average reduction of approximately 55 percent, without increased risk of adverse effects. 

## **11.0 BUDGET:**

**Will any outside organization provide funding or other resources?**

Yes

No

The funding for this study has ended. The PI chooses to continue enrollment for a larger pool for analysis.

